#### 6.4. Subset Analyses

Subset analyses will be performed for OR, DR and PFS per Investigator assessment, and OS based on the FAS for the subgroups defined below.

- MSKCC prognostic criteria at baseline (detailed in Section 6.5.1.3)
  - Favorable (Reference)
  - Intermediate or Poor
- Heng prognostic criteria at baseline (detailed in Section 6.5.1.3)
  - Favorable (Reference)
  - Intermediate
  - Poor

#### 6.5. Baseline and Other Summaries and Analyses

##### 6.5.1. Baseline summaries

The following analyses will be based on the FAS overall and separately by treatment group.

##### 6.5.1.1. Demographic characteristics

Demographic characteristics and physical measurements will be summarized by treatment group using the following information from the ‘Screening/Baseline Visit’ eCRF pages.

- Demographic characteristics
  - Gender: Male, Female
  - Race: White, Black or African American, Asian, American Indian or Alaska Native, Native Hawaiian or other Pacific Islander, Other, Unknown
  - Ethnic origin: Hispanic/Latino (Yes/No)
  - Age (years): summary statistics
  - Age categories :
    - < 65 years, ≥ 65 years
    - <65, 65-<75, 75-<85, ≥ 85
  - Pooled Geographical Region:

- North America
- Europe
- Asia
- Rest of the World (Australasia, Latin America, Africa and/or Middle East will be included as additional pooled geographical regions if including > 10% of the overall treated population)
- Geographic Region (as applicable):
  - North America
  - Latin America
  - Western Europe
  - Eastern Europe
  - Australasia
  - Middle East
  - Asia
  - Africa
- Eastern Cooperative Oncology Group (ECOG) Performance Status: 0, 1, 2, 3, and 4
- Physical measurements
  - Height (cm)
  - Weight (kg)
  - Body Mass Index (BMI) (kg/m^2)
  - Body Surface Area (BSA) (m^2)

Center codes will be used for the determination of the patient's geographic region.

The listing of demographics and baseline characteristics will include the following information: patient identifier, treatment group, age, sex, race, ethnicity, height (cm), weight (kg), BMI (kg/m^2), BSA (m^2) and ECOG performance status.

#### **6.5.1.2. Medical history**

Medical history will be coded using the most current available version of Medical Dictionary for Regulatory Activities (MedDRA) and will be summarized from the 'Medical History' eCRF page. Medical history will be summarized as the numbers and percentages of patients by MedDRA preferred term (PT) as event category and MedDRA primary system organ class (SOC) as summary category. Each patient will be counted only once within each PT or SOC.

Medical history will be displayed in terms of frequency tables: ordered by primary SOC and PT in alphabetical order.

### 6.5.1.3. Disease characteristics

Information on disease characteristics collected on ‘Primary Diagnosis’, ‘Substance Abuse’ and RECIST eCRF pages will be summarized overall and by treatment group. Summary statistics will be presented for the following.

From the ‘Primary Diagnosis’ eCRF page:

- Body side
- Site of primary tumor
- Primary diagnosis (summarize all categories collected in the ‘Primary Diagnosis’ eCRF page)
- Time since initial diagnosis to ‘start date’ (months), defined as (‘start date’ – date of initial diagnosis)/30.4375
- Time since diagnosis of local/regional recurrence of disease (months), defined as (‘start date’ – date of diagnosis of local/regional recurrence of disease)/30.4375
- Time since diagnosis of recurrence/metastatic disease (months), defined as (‘start date’ – date of diagnosis of recurrence/metastatic disease)/30.4375

Memorial Sloan-Kettering Cancer Center (MSKCC) prognostic criteria (Motzer et al., 1999) are based on the detection of five risk factors:

- Karnofsky PS < 80% (since Karnofsky PS is not collected in the eCRF, the derivation of risk factors will use ECOG PS  $\geq 2$  (Oken et al., 1982))
- high LDH (> 1.5 times the ULN)
- serum hemoglobin < LLN
- high corrected serum calcium (> 10 mg/dL)
- prior nephrectomy

According to MSKCC prognostic criteria, patients will be assigned to one of the following risk groups:

- Favorable (0 risk factors)
- Intermediate (1 or 2 risk factors)

- Poor (3 or more risk factors)

Heng prognostic criteria (Heng et al., 2009) are based on the detection of six risk factors:

- Karnofsky PS < 80% (since Karnofsky PS is not collected in the eCRF, the derivation of risk factors will use ECOG PS  $\geq 2$  (Oken et al., 1982))
- high corrected serum calcium ( $> 10$  mg/dL)
- serum hemoglobin < LLN
- time from diagnosis to start of systemic treatment < 12 months
- absolute neutrophils count > ULN
- platelets count > ULN

According to Heng prognostic criteria, patients will be assigned to one of the following risk groups:

- Favorable (0 risk factors)
- Intermediate (1 or 2 risk factors)
- Poor (3 or more risk factors)

From the RECIST eCRF page:

- Measurable disease (lesions) at baseline (Yes, No)
- Involved tumor sites at baseline

From the 'Substance Use' eCRF page:

- Smoking history
  - Never smoker vs current vs former smoker
  - Smoking exposure (pack-years): 0, <20, 20-<40,  $\geq 40$  and summary statistics
  - Years since quitting: never smoker, current smoker, <5, 5-<10,  $\geq 10$  and summary statistics

Specifications for computation:

- Cigarette equivalents are calculated as follows: one cigar is regarded equivalent to 5 cigarettes and 1 pipe is regarded equivalent to 3 cigarettes

- Duration of nicotine consumption [years]:  
 $(\text{end of nicotine consumption} - \text{start of nicotine consumption} + 1) / 365.25$
- Pack-years:
  - calculate cigarette equivalents per day using the conversion factors given above
  - convert to packs per day where 20 cigarettes are regarded as 1 pack
  - pack-years = packs per day  $\times$  duration of nicotine consumption [years]

Listing of disease history will be provided with all relevant data (as collected on the ‘Primary Diagnosis’ and ‘Substance Use’ eCRF pages) and derived variables as above.

#### **6.5.1.4. Prior anti-cancer therapies**

The prior anti-cancer therapies are collected under the ‘Prior Cancer Therapy’, ‘Prior Radiation Therapy’ and ‘Prior Surgery’ eCRF pages.

The number and percentage of patients with at least one prior anti-cancer surgery will be tabulated.

Prior anti-cancer therapies will be included in the listings that follow with a flag to identify prior therapies. These will include the patient identification number, and all the relevant collected data-fields on the corresponding eCRF pages.

- Listing of anti-cancer drug therapies
- Listing of anti-cancer radiotherapy
- Listing of anti-cancer surgeries

#### **6.5.2. Study conduct and patient disposition**

The following analyses will be based on the FAS overall and separately by treatment group.

##### **6.5.2.1. Patient disposition**

The percentages below will be calculated based on the number of patients in the FAS.

- Total number of patients screened overall
- Number of patients who discontinued from the study prior to treatment with study drug overall and by the main reason for discontinuation
- Number and percentage of patients in each of the analysis sets defined in Section 4
- Number and percentage of patients with study drug ongoing (separately for each study drug)

- Number and percentage of patients who discontinued study drug overall and by the main reason for discontinuation of study drug (separately for each study drug)
- Number and percentage of patients who entered follow-up
- Number and percentage of patients who discontinued follow-up overall and by the main reason for discontinuation
- Number and percentage of patients who entered long-term follow-up
- Number and percentage of patients who discontinued long-term follow-up overall and by the main reason for discontinuation

In addition the following will be summarized:

- Number and percentage of treated patients overall, by region (Europe, EEA (required by EudraCT), North America, Latin America, Middle East, Asia, Australasia Africa), by country within region
- Number and percentage of treated patients by center

A cross tabulation of patients who have discontinued/are ongoing treatment with avelumab vs patients who have discontinued/are ongoing treatment with axitinib will also be provided.

#### **6.5.2.2. Protocol deviations**

All protocol violations that impact the safety of the patients and/or the conduct of the study and/or its evaluation will be reported. These include:

- Patients who are dosed on the study despite not satisfying the inclusion criteria;
- Patients who develop withdrawal criteria whilst on the study but are not withdrawn;
- Patients who receive the wrong treatment or an incorrect dose;
- Patients who receive an excluded concomitant medication.
- Deviations from GCP

The identification of these and other CSR-reportable deviations will be based on the inclusion/exclusion criteria or other criteria presented in the protocol.

#### **6.5.3. Study treatment compliance and exposure**

The following analyses will be based on the safety analysis set by treatment group.

Cycle definitions for study drugs that are administered in combination apply to all the study drugs in the combination. Ie, cycle is patient-dependent, rather than study-drug-dependent when study drugs are administered in combination.

For Cycle X, actual cycle start date for each patient is

- the earliest start date of dosing in the Cycle X day 1 visit eCRF exposure page, if the patient received study treatment on that visit (ie, any study drug with dose>0 at that visit)
- the first day of assessments in the Cycle X day 1 visit, if the patient did not receive study treatment on that visit (ie, all study drugs had dose=0 at that visit). Use start date in the exposure page if available; if start date is not available then use date of collection of vital signs on Cycle X day 1 visit.

Actual cycle end date for each patient is,

- for all cycles X except the last cycle, actual cycle end date = actual cycle (X+1) start date – 1 day;
- for the last cycle, actual cycle end date = actual cycle start date + 14 days – 1 day

**Cycle duration** (weeks) = (actual cycle end date – actual cycle start date + 1)/7

When summarizing exposure for each study drug, only cycles from first dose of study treatment until the last cycle with non-zero dose of at least one of the study drugs should be included.

Exposure will be summarized (per cycle and/or overall) as dose received (cumulative dose, actual dose intensity) and as dose received relative to intended dose (relative dose intensity [RDI]).

The derivations below are provided for the following:

- Avelumab administered as a 1-hour IV infusion at a dose of 10 mg/kg or 5 mg/kg once every 2 weeks in 2-week cycles.
- Axitinib administered BID PO at a dose of 5 mg or 3 mg.

Analysis of exposure will be based on the calculated actual dose levels

- Avelumab - total dose / weight
- Axitinib – total dose.

Exposure and compliance will be summarized by cycle (avelumab only) and overall (avelumab and axitinib) for each study drug in each treatment group.

#### **6.5.3.1. Exposure to avelumab**

The dose level for avelumab is calculated as actual dose administered/weight (mg/kg). The last available weight of the patient on or prior to the day of dosing will be used.

**Intended duration of treatment with avelumab** (weeks) =  
(end date–date of first dose of avelumab +1)/7,

where end date = start date of last cycle with non-zero dose of avelumab + 14 – 1

**Duration of exposure to avelumab (weeks) =**

$$(\text{last dose date of avelumab} - \text{first dose date of avelumab} + 14) / 7$$

**Cumulative dose** in a cycle or overall is the sum of the actual dose levels of avelumab received in a cycle or overall, respectively.

**Actual Dose Intensity (DI)**

- By cycle actual DI (mg/kg/2-week cycle) = [cumulative dose in the cycle (mg/kg)]/[cycle duration (weeks)/2]
- Overall actual DI (mg/kg/2-week cycle) = [overall cumulative dose (mg/kg)] / [intended duration of treatment with avelumab (weeks)/2].

**Relative Dose Intensity (RDI)**

- Intended DI (mg/kg/2-week cycle) = [intended cumulative dose per cycle] / [intended number of 2 weeks in a cycle] = [d (mg/kg)] / [1(2-week cycle)] = d (mg/kg/2-week cycle)
- By cycle RDI (%) =  $100 \times [\text{by cycle actual DI}] / [\text{intended DI}]$   
=  $100 \times [\text{by cycle actual DI}] / [d \text{ (mg/kg/2-week cycle)}]$
- Overall RDI (%) =  $100 \times [\text{overall actual DI}] / [\text{intended DI}]$   
=  $100 \times [\text{overall actual DI}] / [d \text{ (mg/kg/2-week cycle)}]$

where d can be 5 or 10.

### 6.5.3.2. Exposure to axitinib

The dose level is calculated as actual dose administered (mg/day).

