5.3.3.2. Axitinib

Axitinib will be administered orally BID at approximately the same time in the morning and evening on a continuous dosing schedule, ie, without a break in dosing in the absence of drug-related toxicity (see [Section 5.3.5](#)). Axitinib tablets are to be taken approximately 12 hours apart and may be administered without regard to meals. Tablets must not be crushed, split, or dissolved, and patients should be instructed to swallow the study medication whole without manipulation or chewing of the medication prior to swallowing.

A dosing card will be provided to the patients to provide guidance for the correct use of axitinib.

Patients must be instructed that if they miss a dose or vomit anytime after taking a dose, they must not "make it up" with an extra dose, but instead resume subsequent doses as prescribed. Any missed dose may be taken late, up to 3 hours before the next scheduled dose of that day, otherwise, it should be skipped and dosing resumed with subsequent doses as prescribed.

Patient must be instructed to record all doses (missed or vomited doses or extra doses) in a dosing diary supplied by the site. If doses are missed or vomited or if an extra dose is taken, this must be indicated in the source documents and CRFs.

If a patient inadvertently takes 1 extra dose during a day, the patient should not take the next dose.

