5.3.5. Recommended Dose Modifications

Every effort should be made to administer investigational product on the planned dose and schedule.

In the event of significant toxicity, dosing may be delayed and/or reduced as described below. In the event of multiple toxicities, dose modification should be based on the worst toxicity observed. Patients are to be instructed to notify investigators at the first occurrence of any adverse symptom. In addition to dose modifications, investigators are encouraged to employ best supportive care according to local institutional clinical practices and according to the guidance for selected adverse events provided below.

For axitinib dose modifications may occur in 2 ways:

- Within a cycle: dosing interruption until adequate recovery and dose reduction, if required, during a given treatment cycle;
- In the next cycle: dose reduction may be required in a subsequent cycle based on toxicity experienced in the previous cycle.

For avelumab, no dose modifications are permitted in this study, but next infusion may be omitted based on persisting toxicity, as outlined in [Table 5](#).

Dose modifications and infusion omissions may occur independently for the two drugs used in this study and will be reported in the CRF.

Available axitinib dose levels for inpatient dose modification are listed in [Table 4](#).

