#### 6.5.3.3. Dose Reductions

Applicable to avelumab. Dose reduction is defined as actual non-zero dose < 90% of the planned dose.

Applicable to axitinib. Dose reduction is defined as a change to a non-zero dose level lower than that planned in the protocol.

The number and percentage of patients with at least one dose reduction as well as a breakdown of dose reductions (1, 2, 3,  $\geq 4$ ) will be summarized.

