#### 6.5.3.4. Dose escalations

Applicable to axitinib only.

Dose escalation is defined as a change to a dose level higher than that planned in the protocol.

The number and percentage of patients with at least one dose escalation as well as a breakdown of dose escalations (1, 2,  $\geq 3$ ) will be summarized.

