#### 6.5.3.5. Dose interruptions

Applicable to axitinib only.

An interruption is defined a 0 mg dose administered on one or more days. What follows defines how dose interruptions will be counted in the case of multiple dose interruptions.

- If an interruption occurs consecutively for at least two days due to the same reason, then it will be counted only once (example: If the actual dose on days 1-3 is 10 mg and actual dose on days 4-5 is 0 mg and dose interruption on days 4-5 is due to AE, then the total number of dose interruptions is 1).
- If an interruption occurs consecutively for at least two days due to different reasons, then it will be counted for each reason (example: If the actual dose on days 1-3 is 10 mg and actual dose on days 4-5 is 0 mg and dose interruption on day 4 is due to AE and dose interruption on day 5 is due to dosing error, then the total number of dose interruptions is 2).
- If an interruption occurs for more than one day due to the same reason, but the days are not consecutive, ie there is at least one dosing day in between, then each dose interruption will be counted as a different occurrence (example: If the actual dose on days 1, 3 and 5, is 10 mg and actual dose on days 2 and 4 is 0 mg, and dose interruptions on day 2 and 4 are both due to dosing error, the total number of dose interruptions is 2).

A dose interruption is not considered a dose reduction.

The number and percentage of patients with dose interruptions and the corresponding reasons will be summarized.

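### Axitinib dose level is defined as actual mg per day, so read literally a single missed dose counts as a dose reduction, and the reduction and escalation summaries mix adherence with prescribed changes

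*SAP*

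**What the plan says.** SAP 6.5.3 sets the basis for the whole exposure section: "Analysis of exposure will be based on the calculated actual dose levels". For axitinib it names the total dose. SAP 6.5.3.2 makes this specific: "The dose level is calculated as actual dose administered (mg/day". The SAP gives no other definition of an axitinib dose level.

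The dose-modification rules follow:

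- **Reduction, axitinib (SAP 6.5.3.3):** "Dose reduction is defined as a change to a non-zero dose level lower than that planned in the protocol".
- **Reduction, avelumab (same section):** "Dose reduction is defined as actual non-zero dose < 90% of the planned dose". Avelumab has a 10% tolerance; axitinib has none.
- **Escalation, axitinib (SAP 6.5.3.4):** "Dose escalation is defined as a change to a dose level higher than that planned in the protocol".
- **Interruption, axitinib (SAP 6.5.3.5):** one or more days at 0 mg. The worked examples use daily totals, for instance "If the actual dose on days 1-3 is 10 mg and actual dose on days 4-5 is 0 mg", and days lost to dosing error are counted.

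Patients with at least one event are tabulated, with a breakdown up to four or more reductions and three or more escalations.

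On data capture, protocol 5.3.3.2 requires: "If doses are missed or vomited or if an extra dose is taken, this must be indicated in the source documents and CRFs". Protocol 5.3.5 separately provides for prescribed changes: "Dose modifications and infusion omissions may occur independently for the two drugs used in this study and will be reported in the CRF". Protocol Table 4 lists the prescribed steps as 10, 7, 5, 3 and 2 mg twice daily.

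**The concern.** A dose reduction table is normally read as showing how often the prescriber had to lower the dose. Here the dose level is what the patient took that day, and the reduction rule applies to any non-zero shortfall. A forgotten evening tablet therefore meets the definition of a reduction, although nobody changed the prescription.

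The ordering is also odd. Missing one of two doses is a reduction, while missing both is only an interruption. A half-missed day is neither at plan nor at 0 mg, so reduction is the only category left for it.

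At stake is the meaning of the axitinib reduction and escalation summaries. If adherence events enter them, a reader could take near-complete exposure for poor tolerability. Two programmers reading the same text could also produce very different tables.

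**Working it through.** **Inputs from the documents.** SAP section 6 states that only DL1, with or without lead-in, was tested, so the plan is 5 mg twice daily, or 10 mg/day. The RDI denominator in SAP 6.5.3.2 uses 7 × 2 × d mg per week, which is 70 mg for d = 5.

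**Reproducing the SAP's own examples.** The only figures given for these rules are the three interruption counts in 6.5.3.5. Applied to daily totals:

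- 10, 10, 10, 0, 0 mg with one reason gives 1 interruption.
- The same days with two different reasons give 2.
- 10, 0, 10, 0, 10 mg gives 2.

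All three match, which confirms that the section works on daily totals.

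**Applying the rules to single dosing events (plan 10 mg/day).**

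| Event | Daily total | Classification |
|---|---|---|
| Both doses taken | 10 mg | at plan |
| One dose missed | 5 mg | reduction |
| Both doses missed | 0 mg | interruption |
| One extra dose, no dose skipped that day | 15 mg | escalation |

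**Illustrating the size.** The documents give no miss rate, so q, the chance that any one dose is missed, is assumed. Misses are taken as independent, there is no prescribed change, and each half-missed day is counted separately.

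- Chance of exactly one miss on a day: p = 2q(1 − q).
- Chance of at least one such day in n days: 1 − (1 − p)^n.
- Expected number of such days: n × p.
- Expected RDI from misses alone: 100 × (1 − q).

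At 26 weeks, n = 26 × 7 = 182:

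| q | p | At least one reduction | Mean count | Expected RDI |
|---|---|---|---|---|
| 0.25% | 0.0049875 | 1 − 0.9950125^182 = 60% | 0.9 | 99.75% |
| 0.5% | 0.00995 | 1 − 0.99005^182 = 84% | 1.8 | 99.5% |
| 1% | 0.0198 | 1 − 0.9802^182 = 97% | 3.6 | 99.0% |

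At q = 1%, the binomial chance of four or more such days by 26 weeks is 49%.

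The result depends on time on treatment. At 4 weeks the chance of at least one reduction is 24% for q = 0.5% and 43% for q = 1%. At 12 weeks it is 57% and 81%.

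**Contrast with RDI.** One missed 5 mg dose in 12 weeks gives RDI = (12 × 70 − 5) / (12 × 70) = 835/840 = 99.4%. Under the literal rule that patient still appears as having had a dose reduction.

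**After the fix.** If only changes of the prescribed dose count, each single missed or extra dose gives 0 reductions and 0 escalations. The RDI is unchanged.

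**The case against.** The best defence is that the SAP does not state this rule outright. The mg/day definition sits in the section that derives cumulative dose and dose intensity, and 6.5.3.3 and 6.5.3.4 do not refer back to it. The avelumab rule speaks of an actual dose, while the axitinib rule speaks of a change to a dose level. The protocol uses dose level for the prescribed Table 4 steps, and a forgotten tablet is not naturally a change of level. This reading is possible, and it is probably what was meant. But the SAP never adopts it, and the only definition the SAP does give says otherwise. The text still needs settling.

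Several limits on the size also stand:

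- Protocol 5.3.3.2 lets a missed dose be taken late, up to 3 hours before the next one, and such a dose need not change the daily total. It also tells a patient who takes an extra dose to skip the next. A reader might infer that every extra dose becomes an escalation; it does so only when the daily total ends above plan.
- The protocol requires missed doses to be indicated in the CRF, but the layout of the dosing page is not available. Whether each half-missed day produces its own record is assumed.
- SAP 6.5.3.3 does not say how consecutive below-plan days are counted. This affects the four-or-more category, but not the share with at least one.
- If misses are concentrated in a few patients, the share with at least one is lower than the independent-miss figures.

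A reader might also infer that the table measures adherence instead of toxicity management, so that toxicity-driven reductions are hidden. The documents do not support that. Prescribed reductions are still counted in 6.5.3.3, so the table is a mixture. SAP 6.6.1 takes adverse events leading to dose reduction from the action recorded on the AE page, and 6.6.1.1 to 6.6.1.3 tabulate reductions and interruptions on that basis without using mg/day.

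**Conclusion.** The point holds as a defect of definition in two descriptive summaries. Applied as written, SAP 6.5.3.2 to 6.5.3.4 classify a half-missed day as an axitinib dose reduction and an uncompensated extra dose as an escalation. Both summaries would then mix adherence with prescribed changes.

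The classification follows from the text. The size does not. The 60%, 84% and 97% at 26 weeks rest on assumed miss rates of 0.25%, 0.5% and 1%, independence, separate recording of each such day and no prescribed change. They show that low miss rates are enough to dominate the table; they do not predict this trial.

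One further inference should be resisted: that the defect bears on the choice of the RP2D. No section ties the 6.5.3.3 count to that decision. Protocol 3.4 refers to feasibility of long-term administration and singles out discontinuation due to treatment-related adverse events; protocol 3.1.1.2 refers generally to the MTD, safety, efficacy, PK and pharmacodynamics. Dose finding was already complete at SAP version 2. The DLT, MTD and efficacy analyses do not use these tables.

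**What to change.** In SAP 6.5.3.3 and 6.5.3.4, define an axitinib reduction or escalation as a change in the prescribed twice-daily dose recorded in the CRF, using the protocol Table 4 levels. State that days with a single missed, vomited or extra dose are not counted there and stay in cumulative dose and RDI, where they already enter. Keep the mg/day definition in 6.5.3.2 for those exposure measures only.

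The cost is a few sentences in the SAP and one derivation. No new data are needed, because the protocol already requires dose modifications to be reported in the CRF.
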